### **11.5.3 Per Protocol (PP) Analysis Set**

The per protocol (PP) analysis set will consist of all subjects from the FAS without any major protocol violations. The PP analysis set will be used for a sensitivity analysis of the primary endpoint.

## **11.6 Statistical Methods**

### **11.6.1 Randomization**

This is a one arm study thus no randomization will be performed.

### **11.6.2 Disposition of Subjects/Data**

The numbers of subjects who were enrolled will be provided. A list of discontinued subjects together with the reasons for discontinuation will be presented.

### **11.6.3 Demographic and Baseline Characteristics**

Demographic and baseline characteristics including age, gender, race, ethnicity, height, weight and BMI will be tabulated. Continuous variables will be summarized by a mean, standard deviation, minimum, median and maximum, and categorical variables by a count and percentage.

### **11.6.4 Efficacy Analyses**

All efficacy analyses will be performed on the FAS. All efficacy endpoints will be listed by subject and presented descriptively.

### **11.6.5 Safety Analyses**

All safety analyses will be performed on the Safety Analysis Population. The safety assessment will be based on the incidence, severity and relationship to treatment of the adverse events.

All Serious Adverse Events (SAEs) will be listed and discussed on a subject-by-subject basis.

Vital signs will be presented descriptively by visit.

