### 10.2 Withdrawal from the study

A subject will be withdrawn from the study for any of the following reasons:

- Withdrawal of consent
- Subject is not compliant with requirements of the study, including inclusion and exclusion criteria.
- The investigator believes that for safety reasons (e.g. an adverse event) it is in the best interest of the patient to stop the study.
- The study is prematurely stopped or halted (e.g. clinical halt)

Subjects enrolled in the study can discontinue their participation at any time for any reason without prejudice or reduction in the quality of their medical care. The investigators or sponsor can terminate a subject's participation in this study to protect the subject's health or if the subject fails to follow directions resulting in noncompliance to study procedures. Subjects who fail to complete the study will be replaced and will not be considered evaluable.

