## **11.4 Sample Size Determination**

A total samples size of 70 subjects should be enrolled into the study.

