## **11.5 Analysis Data Sets**

### **11.5.1 Safety Analysis Set**

All subjects who received treatment will be included in the safety analysis set. The safety analysis set will be used for the summary and analyses of all safety endpoints.

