## 13 RISK / BENEFIT ANALYSIS

### 13.1 Risks

The BeShape One Device is a high-intensity non focused ultrasound device intended for non-invasive waist circumference reduction in adult population. The risks to patients resulting from potential device hazards and associated with the study procedures/devices have been analyzed using the Risk Management Standard - ISO 14971. The different types of hazards were identified and evaluated using risk assessment numerical parameters. Applicable controls for the risks were analyzed. After the implementation of appropriate risk control measures, the level of risk was re-evaluated and found to be acceptable. Below is a summary of some of the key hazards and applicable control measures.

**Patient Injury Risk:** The BeShape One device may cause over-heating related patient injuries such as skin burns, blistering and erythema.

**Patient Injury Risk Mitigation:** The over-heating related injuries are mitigated by an inherent device design cooling mechanism and controlling mechanism that stops activation of the device at a predetermined time. In addition, mitigation is achieved by comprehensive software validation ensuring correct device algorithm output, including constant monitoring of the energy level during treatment and cooling water and therapeutic heating temperature control. The device has also been tested in pre-clinical settings, demonstrating and proving the safety of the device.

**Biocompatibility Risk:** The device components and/or materials may present a biocompatibility risk (irritation, allergic reaction, etc.) if they contact the patients' body.

**Biocompatibility Risk Mitigation:** The risk of biocompatibility is mitigated as all the materials that come in contact with the skin human are known to be biocompatible. The device is non-invasive and only comes in contact with the outer skin surface.

**Use Risk:** The operator may perform the treatment incorrectly (due to use error or SW bug) and/or apply excessive treatment duration, potentially causing patient injury.

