**Use Risk Mitigation:** The BeShape One device includes a floor standing portable console and touch screen which indicates if the acoustic energy is turned on or off. The user can stop the acoustic energy transmission at any time by pressing the on/off button or the emergency button. Furthermore, prior to each treatment a system test is performed. Comprehensive software validation, proper operator training, proper instructions for use and electrical safety testing are additional mitigations for this use risk.

**Performance Risk:** The BeShape One device may lead to ineffective treatment due to vacuum mechanism failure.

**Performance Risk Mitigation:** This risk is mitigated by real time monitoring of the vacuum level and software control on energy transmission coupled to vacuum formation. The system is configured to stop its operation if good skin contact is not established. Further mitigations include pre-clinical studies and SW validation.

**System Failure Risk:** The BeShape One device may fail to operate due to system malfunction.

**System Failure Risk Mitigation:** The BeShape Once device is calibrated during manufacturing. In addition, the manufacturer supplies it with a tissue-mimicking phantom for periodic user tests.

In summary, there are no anticipated severe risks or serious adverse device effects. There are no contraindications for use in the proposed study or study population. There may be other risks to the subject that are associated with the device or procedure which are unforeseeable at this time.

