## 13.2 Benefits

Subjects may or may not benefit from circumferential waist reduction of the treated area resulting in body contouring improvement via the investigational device. Subjects will receive all treatment procedures at no cost. This study will benefit the advancement of medicine by generating data on safety and efficacy that will aid in the development of an alternative treatment options to procedures with higher potential risks, such as liposuction. The results of this study will help to determine whether this device is safe and effective for improvement of waist circumference reduction.

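### Section 11.6.5 plans no measure of precision for adverse-event rates, so a zero or low count in about 70 treated subjects would not show which true rates remain compatible with it

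*Combined protocol and SAP*

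**What the plan says.** Sections 5 and 11.1 of the combined protocol and SAP put safety in the study objective beside efficacy or performance. Section 13.2 describes the use of the data: "The results of this study will help to determine whether this device is safe and effective".

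The analysis is in Section 11.6.5: "The safety assessment will be based on the incidence, severity and relationship to treatment of the adverse events". For serious events it adds: "All Serious Adverse Events (SAEs) will be listed and discussed on a subject-by-subject basis". Vital signs are summarised by visit. The denominator is set in Section 11.5.1: "All subjects who received treatment will be included in the safety analysis set".

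Section 11.4 gives the size of the study without any derivation: "A total samples size of 70 subjects should be enrolled into the study". Section 10.2 adds: "Subjects who fail to complete the study will be replaced and will not be considered evaluable".

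On expected harms, Section 13.1 says the device "may cause over-heating related patient injuries such as skin burns, blistering and erythema", describes the controls against this, and concludes: "In summary, there are no anticipated severe risks or serious adverse device effects". It also allows that there may be risks not yet foreseen.

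Neither Section 11.6.5 nor any other section gives a confidence interval, an upper limit, an acceptable rate or a decision criterion for any adverse event.

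**The concern.** With no comparator, the quantitative safety evidence is the observed per-subject rate and its uncertainty. The plan provides for the first and not the second.

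This matters most when the count is zero or very low. For serious device effects, zero is what Section 13.1 leads the reader to expect. With no events there is no severity to grade, no relationship to assign and no case to discuss, so the other parts of the safety assessment add nothing on that outcome. Only an upper limit then conveys information. For an elective procedure in volunteers, a rate of a few per cent and a rate near zero are different findings, and the planned report would not show which of them the data can separate.

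**Working it through.** **Inputs**
- Number treated: n = 70 (Section 11.4), assuming that every enrolled subject is treated. Section 11.5.1 makes treated subjects the denominator.
- Expected serious device effects: none (Section 13.1). No numerical rate is given.
- Confidence level: not stated in the documents. I assume 95% and show both conventions.

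The plan's figure of 70 cannot be reproduced. Section 11.4 comes with no error rate, power, effect size, standard deviation or event rate.

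**Upper limit with zero events**

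The exact (Clopper-Pearson) limit solves (1 − p)^n = a, so p = 1 − a^(1/n).
- Two-sided 95%, a = 0.025: 1 − 0.025^(1/70) = 0.0513, or 5.1%.
- One-sided 95%, a = 0.05: 1 − 0.05^(1/70) = 0.0419, or 4.2%.
- Cross-checks: the rule of three gives 3/70 = 4.3%, close to the one-sided limit. The Wilson two-sided limit, 1.96²/(70 + 1.96²), is 5.2%.

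**Low counts other than zero**

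Exact two-sided 95% upper limits in 70 subjects, from the 0.975 quantile of Beta(x + 1, 70 − x), are 7.7% for 1 event, 9.9% for 2 and 12.0% for 3.

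**How often a study of 70 would show nothing**

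P(0 events) = (1 − p)^70.

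| True rate | P(0 of 70) |
|---|---|
| 1% | 49% |
| 2% | 24% |
| 3% | 12% |
| 4% | 5.7% |
| 5% | 2.8% |

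**Sensitivity to the number treated**

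Section 10.2 replaces non-completers while Section 11.5.1 keeps every treated subject, so the safety set can exceed 70. It could also fall short if fewer subjects are treated. Upper limits with zero events:

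| n treated | Two-sided 95% | One-sided 95% |
|---|---|---|
| 60 | 6.0% | 4.9% |
| 65 | 5.5% | 4.5% |
| 70 | 5.1% | 4.2% |
| 75 | 4.8% | 3.9% |
| 80 | 4.5% | 3.7% |

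Over this range the two-sided limit stays between 4.5% and 6.0%. The message does not depend on exactly 70 being treated, but the reported figure does.

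**The case against.** The strongest reply is that descriptive safety tables are an ordinary choice in a small one-arm study. The primary endpoint and the only hypothesis concern waist circumference (Sections 11.2.1 and 11.3), and safety carries no hypothesis. Sections 14.2.1 and 15.4 place the study under the rules for non-significant-risk devices. Nothing suggests that 70 was chosen to exclude a given rate of serious events. Anyone with the count and the denominator can compute the interval later, from the same data.

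Much of this stands. It limits the point to an improvement in reporting, because the data collected and the point estimates are unaffected. It does not remove the gap. An interval is an estimate and needs no hypothesis or extra subjects. Naming the outcomes to be bounded beforehand also prevents event categories from being grouped or split once the data are known, which a reader's later calculation cannot do.

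It is also fair that this is one instance of a wider lack of planned estimation. Section 11.6.4 presents even the primary endpoint only descriptively, despite the hypothesis in Section 11.3.

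Three stronger readings are tempting, and the documents do not support them:
- *Zero events will be reported as proof of safety.* No section contains such a rule. Section 13.2 says only that the results will contribute to a determination.
- *Safety rests on crude incidence alone.* Section 11.6.5 also covers severity, relationship, case-by-case discussion of serious events and vital signs, and Section 8 requires skin checks during treatment. None of these bounds a rate, but they are part of the assessment.
- *The expected zero applies to burns as well.* Section 13.1 anticipates no serious device effects. Burns, blisters and erythema need not be serious under Section 12.1, and nothing shows that a zero count of skin reactions is likely. The zero-event calculation applies chiefly to rare serious events; for burns or blisters the limits for one to three events may be the relevant ones.

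**Conclusion.** The point holds as a gap in precision. As written, the safety results of a one-arm study of about 70 subjects would carry no statement of which rates of device-related injury remain compatible with a zero or low count. For the expected result on serious device effects, 0 of 70, the data would be compatible with true rates up to 5.1% (exact two-sided 95%) or 4.2% (one-sided 95%). A single event would raise the two-sided limit to 7.7%.

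These figures assume 70 treated subjects, independent events between subjects and a 95% level that the documents do not specify. The final limit must come from the number actually treated, so 5.1% cannot be carried into the report as a fixed value. The gap does not invalidate the study. It affects what the safety conclusion can claim, and it is a cheap improvement rather than a defect in design.

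**What to change.** In Section 11.6.5, add that the number and percentage of subjects with each of the following will be reported, each with an exact (Clopper-Pearson) two-sided 95% confidence interval based on the actual number treated in the safety set:

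(a) any device-related adverse event, stating which relationship categories of Section 12.3 count as device-related;
(b) a burn or blister;
(c) a serious adverse device effect.

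State that the safety conclusion will be worded by the resulting upper limits, so that a zero count is reported together with the rate it excludes.

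Section 11.4 may add, as illustration only, that zero events in 70 treated subjects would give an upper limit of about 5.1% (two-sided 95%).

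The cost is a few lines of SAP text and one more column in the safety table. Sample size, visits and data collection do not change. The downside for the sponsor is a less favourable safety statement.

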## **12 SAFETY, ADVERSE EVENT AND DEVICE DEFICIENCY REPORTING**

Timely, accurate, and complete reporting and analysis of safety information from clinical studies are crucial for the protection of subjects, investigators, and the sponsor and are mandated by regulatory agencies worldwide. The sponsor has established Standard Operating Procedures (SOPs) in conformity with regulatory requirements worldwide to ensure appropriate reporting of safety information. All clinical studies conducted by the sponsor or of its affiliates will be conducted in accordance with those procedures.

### **12.1 Definitions**

The definitions provided below are in compliance with ISO 14155 (2020-07 third edition) and 21 CFR 812.3

- Adverse Event (AE)**

An adverse event is any untoward medical occurrence, unintended disease or injury, or untoward clinical signs in subjects, users or other persons, whether or not related to the investigational medical device and whether anticipated or unanticipated.

This definition includes any occurrence that is new in onset or aggravated in severity or frequency from the baseline condition, or abnormal results of diagnostic procedures, including laboratory test abnormalities.

This definition also includes events related to the control and to the procedures involved.

Note: The sponsor collects adverse events starting with the signing of the informed consent.

- **Adverse Device Effect (ADE)**

An adverse event related to the use of an investigational medical device.

This definition includes adverse events resulting from insufficient or inadequate instructions for use, deployment, implantation, installation or operation or any malfunction of the investigational device.

This definition includes any event resulting from use error or from intentional misuse of the investigational device.

- **Serious Adverse Event (SAE)**

An adverse event that led to any of the following:

- death
- serious deterioration in the health of the subject, users or other persons as defined by one or more of the following:
  - a life-threatening illness or injury or a permanent impairment of a body structure or
  - a body function including chronic diseases or
  - in-patient or prolonged hospitalization or
  - medical or surgical intervention to prevent life-threatening illness or injury or permanent impairment to a body structure or function
- foetal distress, foetal death, a congenital abnormality, or birth defect including physical or mental impairment

Note: Medical and scientific judgment should be exercised in deciding whether expedited reporting is also appropriate in situations other than those listed above. For example, important medical events may not be immediately life threatening or result in death or hospitalization but may jeopardize the subject or may require intervention to prevent one of the outcomes listed in the definition above. Any adverse event is considered a serious adverse event if it is associated with clinical signs or symptoms judged by the investigator to have a significant clinical impact.

- **Serious Adverse Device Effect (SADE)**

An adverse device effect (ADE) that has resulted in any of the consequences characteristic of a serious device event (SAE).

- **Unanticipated Serious Adverse Device Effect (USADE)**

A serious adverse device effect (SADE) which by its nature, incidence, severity or outcome has not been identified in the current version of the risk assessment.

Note: Anticipated serious adverse device effect (ASADE) is an effect which by its nature, incidence, severity or outcome has been identified in the current version of the risk assessment.

- **Device Deficiency (DD)**

Inadequacy of a medical device with respect to its identity, quality, durability, reliability, usability, safety and performance.

This definition includes malfunctions, use errors and inadequacy in the information supplied by the manufacturer including labeling.

This definition includes device deficiencies related to the investigational device or control.

## **12.2      Definition of Adverse Event Severity**

For all adverse events, the severity of the adverse event will be determined by the investigator, using the following terms:

- **Mild**

A mild adverse event is one in which the subject is aware of the event, but it is easily tolerated without intervention.

- **Moderate**

A moderate adverse event is one that causes sufficient discomfort to interfere with usual activities.

- **Severe**

A severe adverse event is one that results in the inability to perform usual activities.

## **12.3      Definition of Relationship to Investigational Device**

For all adverse events, the relationship to study device and/or procedure will be determined by the investigator, using the following terms:

- **Probably related:**

Follows a reasonable temporal sequence from study device delivery / retrieval, and cannot be reasonably explained by known characteristics of the patient's clinical data or the surgical procedure applied.

- **Possibly related:**

Follows a reasonable temporal sequence from study device delivery / retrieval, but could have been produced by the patient's clinical state or by the surgical procedures regardless of the study device.

- **Probably not related:**

Temporal association is such that the study device is not likely to have had any reasonable association with the observed event.

- **Not related:**

No relationship to study device activation is perceived.

## **12.4 Management of Adverse Events**

### **12.4.1 Adverse Events Assessments**

Should the subject experience an adverse event, an assessment of the situation will be initiated by the study staff, the PI will be notified and appropriate course of action will be determined. The sponsor will be contacted as appropriate. The AE will be documented and reported per the sponsor SOPs, IRB and regulation requirements.

### **12.4.2 Adverse Event Documentation**

The adverse event will be recorded in the Case Report Forms and will include the following information:

- Type of effect (AE, ADE, SAE, UADE, ASADE, SADE)
- Date of onset and resolution
- Severity
- Seriousness (yes/no)
- Relationship to device/procedure
- Anticipated (yes/no)
- Treatment given and/or action taken

### **12.4.3 Reporting of SAE and/or UADE**

All SAE's, SADE, ASADE and UADE will be reported in writing to the PI, sponsor and IRB within 72 hours of knowledge of the event.

If the event resulted in death of a subject, the event will be reported to the PI, sponsor and IRB within 24 hours of knowledge of the event.

In case of an UADE, the sponsor will immediately conduct an evaluation. The results of the evaluation will be reported to the regulatory authorities, IRB and PI within 10 days after the sponsor first receives notice of the effect.

## **12.5 Management of Device Deficiencies**

### **12.5.1 Device Deficiency Assessment**

All DD of an investigational device will be documented throughout the study and managed by the sponsor in accordance with written SOPs for the control of a non-conforming product. The sponsor will take, where applicable, appropriate corrective and preventive actions to protect the safety of subjects, users and other persons. Device deficiencies of the control, if applicable, will also be documented.

### **12.5.2 Device Deficiency Documentation**

The PI will record any observed device deficiency on a device deficiency form. The form may or may not be part of the CRFs.

The sponsor will review all device deficiencies and determine and document in writing whether they could have led to a serious adverse device effect.

### 12.5.3 Reporting of Device Deficiencies

The PI will report to the sponsor, IRB and regulatory authorities (if applicable) device deficiencies that could have led to a serious adverse device effect within 72 hours of knowledge of the event.

## 13 RISK / BENEFIT ANALYSIS

### 13.1 Risks

The BeShape One Device is a high-intensity non focused ultrasound device intended for non-invasive waist circumference reduction in adult population. The risks to patients resulting from potential device hazards and associated with the study procedures/devices have been analyzed using the Risk Management Standard - ISO 14971. The different types of hazards were identified and evaluated using risk assessment numerical parameters. Applicable controls for the risks were analyzed. After the implementation of appropriate risk control measures, the level of risk was re-evaluated and found to be acceptable. Below is a summary of some of the key hazards and applicable control measures.

**Patient Injury Risk:** The BeShape One device may cause over-heating related patient injuries such as skin burns, blistering and erythema.

**Patient Injury Risk Mitigation:** The over-heating related injuries are mitigated by an inherent device design cooling mechanism and controlling mechanism that stops activation of the device at a predetermined time. In addition, mitigation is achieved by comprehensive software validation ensuring correct device algorithm output, including constant monitoring of the energy level during treatment and cooling water and therapeutic heating temperature control. The device has also been tested in pre-clinical settings, demonstrating and proving the safety of the device.

**Biocompatibility Risk:** The device components and/or materials may present a biocompatibility risk (irritation, allergic reaction, etc.) if they contact the patients' body.

**Biocompatibility Risk Mitigation:** The risk of biocompatibility is mitigated as all the materials that come in contact with the skin human are known to be biocompatible. The device is non-invasive and only comes in contact with the outer skin surface.

**Use Risk:** The operator may perform the treatment incorrectly (due to use error or SW bug) and/or apply excessive treatment duration, potentially causing patient injury.

**Use Risk Mitigation:** The BeShape One device includes a floor standing portable console and touch screen which indicates if the acoustic energy is turned on or off. The user can stop the acoustic energy transmission at any time by pressing the on/off button or the emergency button. Furthermore, prior to each treatment a system test is performed. Comprehensive software validation, proper operator training, proper instructions for use and electrical safety testing are additional mitigations for this use risk.

**Performance Risk:** The BeShape One device may lead to ineffective treatment due to vacuum mechanism failure.

**Performance Risk Mitigation:** This risk is mitigated by real time monitoring of the vacuum level and software control on energy transmission coupled to vacuum formation. The system is configured to stop its operation if good skin contact is not established. Further mitigations include pre-clinical studies and SW validation.

**System Failure Risk:** The BeShape One device may fail to operate due to system malfunction.

**System Failure Risk Mitigation:** The BeShape Once device is calibrated during manufacturing. In addition, the manufacturer supplies it with a tissue-mimicking phantom for periodic user tests.

In summary, there are no anticipated severe risks or serious adverse device effects. There are no contraindications for use in the proposed study or study population. There may be other risks to the subject that are associated with the device or procedure which are unforeseeable at this time.

